2.3 PARTICIPANT REGISTRATION AND STATUS UPDATE PROCEDURES

Registration and status updates (e.g., when a participant is taken off protocol therapy and when a participant is taken off-study) will take place per CCR SOP ADCR-2, CCR Participant Registration & Status Updates found at:

<https://ccrod.cancer.gov/confluence/pages/viewpage.action?pageId=73203825>.

2.3.1 Treatment Assignment Procedures (for registration purposes only)

Cohorts

Number	Name	Description
1	Lead-In Cohort (closed December 2018)	Participants with advanced castration resistant prostate cancer (first six participants)
2	Biochemical Recurrence Cohort	Participants with biochemically recurrent prostate cancer

Arms

Number	Name	Description
1	Combination therapy (closed December 2018)	Prostvac + CV301 + MSB0011359C
2	Combination therapy + surveillance (closed)	Surveillance followed by Prostvac + CV301 then Prostvac + CV301 + MSB0011359C
3	Combination vaccine therapy +/- surveillance	Surveillance as needed followed by Prostvac + CV301

Arm Assignment

Participants in cohort 1 will be directly assigned to Arm 1 of the study. This cohort has been closed as of December 2018.

Participants in cohort 2 will be directly assigned to Arm 2, or Arm 3 of the study based upon time of enrollment. Participants enrolling after approval of amendment dated 7/29/2021 are assigned to Arm 3.

Please note: As of December 21, 2018, the 6 participants in the lead in cohort have completed the 6-week toxicity assessment period and no SAEs were seen. Per the protocol design participants will now be enrolled to the BCR cohort. The toxicity assessment of participants in the lead-in cohort is described in section [1.2.13](#).

2.4 BASELINE EVALUATION

- A. The following parameters will be obtained **within 8 weeks** prior to enrollment:
 1. Baseline electrocardiogram (EKG) on all participants, and appropriate cardiologic evaluation, as clinically indicated, to provide baseline function and identify any participants who should be monitored closely for cardiac risks associated with vaccinia vaccination.
- B. The following parameters will be obtained **within 16 days** prior to start of treatment (these tests will not need to be repeated if they were done at screening within the appropriate timeframe):
 1. Clinical evaluation
 - History and physical examination

- ECOG performance status (see **APPENDIX A**)
- Height, weight

2. Laboratory studies

- Serum PSA
- Serum testosterone level
- CBC/differential, with platelet count
- Serum chemistries (Na⁺, K⁺, Cl⁻, CO₂, glucose, BUN, creatinine, albumin, calcium, magnesium, phosphorus, alkaline phosphatase, ALT, AST, total bilirubin, LDH, CK, uric acid, total protein)
- Serum amylase and lipase
- Serum thyroid stimulating hormone (TSH)
- Lymphocyte phenotyping CD3/CD4/CD8
- Urinalysis in participants unless not feasible (i.e.. participant has incontinence)
- Prostate acid phosphatase (PAP)

3 STUDY IMPLEMENTATION

3.1 STUDY DESIGN

This is a three-arm, open-label trial of combination immunotherapy in participants with biochemical recurrent prostate cancer. 37 evaluable participants will be enrolled (after the Safety Lead-In cohort with 6 participants (arm 1), 6 participants who received M7824 as part of the initial investigation for PSA response (arm 2), and 25 homogenously treated participants (arm 3) with an accrual ceiling of 40 participants.

A 6-participant phase I lead in cohort in advanced castration resistant prostate cancer participants will be conducted to determine safety. Dose levels for the lead in cohort are equivalent to the biochemical recurrence cohort. Participants will not have an observation period for the safety lead-in; dosing will begin after eligibility is confirmed (see Study Calendar in Section **18.2**).

Once all 6 participants have completed a 6-week toxicity assessment period the toxicity data will be shared with IRB before moving forward with the planned study in biochemical recurrence.

Participants may remain on treatment with vaccines in the lead in cohort as long as the participant is willing and their disease remains stable on follow-up imaging. As of December 21, 2018, the 6 participants in the lead in cohort have completed the 6-week toxicity assessment period and no SAEs were seen; therefore this cohort is closed.

Participants enrolled in Cohort 2 will undergo surveillance with four consecutive monthly PSA checks followed by Prostvac and CV301 during months 1-4 then Prostvac and CV301 during months 5-7.

- Existing participants with biochemical recurrent prostate cancer undergoing surveillance and PSA monitoring at the NIH may be enrolled at any point during the surveillance period provided the PSA monitoring is consistent with PSA monitoring in the Study Calendar (**APPENDIX C**) and the participant meets all other eligibility criteria. For example, if an eligible participant has 3 monthly PSA values, he may be enrolled onto the study, obtain one additional PSA value at a one month interval to complete the surveillance period, then

begin C1D1 with vaccine therapy. In this case, the 3 PSA values obtained prior to enrollment will be evaluated as if they were collected during the surveillance period while enrolled and will factor into the determination of the intra-study apex value (See Section 6.3.2) highest PSA that is within 10% of another peak PSA for the participant on-study. Any other peak PSA values that are beyond 10% of other PSA values on the study will be determined as potential lab variability and excluded from response assessment.

- With Amendment v05/10/2023, participants that have at least 3 PSA measurements in the surveillance period, with at least one of them sufficient to provide the doubling time from baseline, will not undergo any further PSA measurements in the surveillance period.

Prostvac will be administered nearly identical to the Phase III dosing with Prostvac-V given day 1 (week 1) followed by Prostvac-F on weeks 3 and 5 then monthly for an additional 5 months. Therefore, Prostvac-V is given one time (priming vaccine) followed by 7 doses of Prostvac-F (booster vaccine). The administration schema for CV301 is representative of the Phase I dose escalation trial. MVA-BN-CV301 (priming vaccine) is administered on day 1 (week 1) and week 3 followed by FPV-CV301 (booster vaccine) administered on week 5 then monthly for an additional 5 months.

MSB0011359C (anti-PDL1 TGF β Trap) will be administered at the recommended phase II dose of 1200mg by IV infusion every 2 weeks for 3 months (6 doses) starting after 4 months of concurrent Prostvac and CV301.

Effective with amendment v7/29/2021, MSB0011359C will no longer be given as part of the treatment combination for the Biochemical Recurrence cohort (Arms 2 and 3). This cohort will now receive Prostvac and CV301 during months 1-7 following surveillance.

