6.3.2 Intra-study PSA response

Participants will be monitored for PSA kinetics once enrolled. Participants who have an intra study decline in PSA will be evaluated for PSA response. Such responses would be defined by an intra-study apex PSA, which will be established by determining the maximum PSA value that can be validated by another intra-study PSA value within 10%. (The goal here is to not capture lab variations which may be seen as isolated PSA spikes (i.e. greater than 10%) in the context of participant follow-up. Responders will then be evaluated using confirmed PSA declines (at least 2 consecutive values after the intra-study apex) of at least 30%. Participants with intra-study PSA declines greater than 50% will also be identified.

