10.2 SAMPLE SIZE DETERMINATION

The trial will begin with a 6-participant safety lead-in. Following determination of safety, the primary objective of this study is to determine if the use of two vaccines combined with an immune checkpoint inhibitor can be associated with a modestly high fraction of participants who can experience at least a 30% decline from their maximum PSA anytime during treatment to the minimum value during treatment.

Safety data for the 6-participant lead-in will be shared with IRB before accrual commences in the biochemical recurrence cohort. Beyond safety, this cohort will just be evaluated in a descriptive manner.

Because participants may be receiving the proposed treatment and be followed for PSA changes over an extended period, and the evaluation of the endpoint may take place at any point during this potentially long period, the trial will use a single stage design for evaluating efficacy. With 25 evaluable participants who do not receive M7824, there would be 82% power to rule out 15% and be consistent with 35% who may be able to experience a 30% decline in PSA, using an exact binomial test with a 0.10 one-sided significance level. As an illustration, if 25 evaluable participants are enrolled, 7 of 25 (28.0%) who experience at least a 30% PSA change from the maximum level would have an associated one-sided lower 90% confidence interval bound of 16.3%, and simultaneously an associated one-sided upper 90% confidence interval bound of 42.6%. These demonstrate that 7/25 would be a desirable result based on the parameters selected.

With the amendment v7/29/2021, the initial 6 participants who received M7824 will be evaluated separately in exploratory fashion and will not be included among the 25 main participants.

In addition, because a trial of participants with similar eligibility (16-C-0035) may result in approximately 36 participants who are undergoing surveillance for 6 months, this other trial may serve as a control for a secondary evaluation. The changes in PSA on this trial during the initial 6 months can be compared to the changes in PSA during the initial 6 months on the surveillance arm of the control trial as a secondary evaluation. With 25 evaluable participants on this trial and 36 evaluable participants on the other trial, there would be 81% power to identify a difference between 35% of participants on this trial with a 30% PSA maximum change and 10% of participants on the

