10.4 STATISTICAL ANALYSES

10.4.1 General approach

Following a safety determination in 6 participants meeting separate eligibility requirements, the PSA decline measured from the maximal value obtained while on study to the minimum value obtained while on study will be obtained for each patient, and will be considered a success if the maximal PSA decline is 30% or more. The fraction of evaluable participants who experience at least a 30% decline will be determined. Quantitative parameters will be tested for changes over time using paired tests.

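### The primary PSA response is defined on two time windows, and the wider one lets falls before the first vaccine count against a 15% null set beside a treatment-only definition

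*Combined protocol and SAP*

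**What the plan says.** **Treatment window.** Section 10.2 describes the objective as "at least a 30% decline from their maximum PSA anytime during treatment to the minimum value during treatment". The same section sets the design. "With 25 evaluable participants who do not receive M7824", it tests 15% against 35% "using an exact binomial test with a 0.10 one-sided significance level", with 82% power. It illustrates success with 7/25, whose one-sided 90% bounds it gives as 16.3% and 42.6%.

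**On-study window.** Section 10.4.1 scores "the PSA decline measured from the maximal value obtained while on study to the minimum value obtained while on study". Section 10.4.2 uses the same window for the primary analysis, with two-sided 80% and 95% intervals.

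**Apex.** Section 6.3.2 begins "Participants will be monitored for PSA kinetics once enrolled". It takes the apex as the highest intra-study PSA supported by another within 10%, and asks for two consecutive later values at least 30% lower. It does not mention the date of the first vaccine.

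**Values before treatment.** Section 3.1 gives the example of a man with three monthly values before he enrols: "the 3 PSA values obtained prior to enrollment will be evaluated as if they were collected during the surveillance period while enrolled". It adds that these values help to determine the apex. The calendar in Appendix C (18.1) places up to four surveillance PSA values before C1D1.

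**Values after treatment.** Section 3.7 and the same calendar continue PSA measurement in follow-up, so the on-study window also has no stated end.

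**Untreated rate.** The only figure is a planning input for the secondary comparison in 10.2: "difference between 35% of participants on this trial with a 30% PSA maximum change and 10% of participants on the" control trial (16-C-0035), over 6 months of surveillance.

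**The concern.** The objective in 1.1.1 is whether the immunotherapy can induce a 30% decline. A fall before the first dose cannot be induced by it, yet nothing in 3.1, 6.3.2, 10.4.1 or 10.4.2 requires the apex or the lower values to come at or after C1D1. The confirmation rule in 6.3.2 does not prevent this, because a validated and confirmed fall can lie wholly or partly in surveillance.

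Two things are at stake. Two analysts, one following 10.2 and the other 10.4.2, could classify the same man differently on the only primary test. And if the 15% describes the treatment window, scoring a longer window against it raises the chance that an inactive vaccine passes. Arm 3 has no concurrent control, so nothing else in the primary analysis would reveal this.

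**Working it through.** **Inputs.** N = 25, null 15%, alternative 35%, one-sided 0.10, and 7/25 as a desirable result (all 10.2); surveillance of up to 4 months (Précis, Appendix C); 7 months of vaccine (Appendix C); untreated planning rate of 10% per 6 months (10.2). Not in the documents: how the 15% was derived, and how often a 30% fall occurs in surveillance. The second is treated below as an assumption, with a range.

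**1. The plan's own figures.** With X ~ Binomial(25, p):
- P(X ≥ 7 | 0.15) = 0.0695, and P(X ≥ 6 | 0.15) = 0.1615, so 7 is the correct cut-off for 0.10.
- P(X ≥ 7 | 0.35) = 0.827, against the stated 82%.
- Exact one-sided 90% bounds for 7/25 are 16.3% and 42.6%, as stated. The lower limit of the two-sided 80% interval in 10.4.2 is the same 16.3%, so that interval is equivalent to the 0.10 test.

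The design figures are correct for a true null of 15%.

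**2. Direction.** Read the endpoint as a maximum followed by a later minimum. Adding values before C1D1 can leave the maximum unchanged or replace it with an earlier, higher one. The values that followed the old maximum still follow the new one, and they lie at least as far below it. The response rate of an inactive vaccine can therefore only stay the same or rise.

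**3. Sensitivity of the 7/25 rule.** P(X ≥ 7 | p) reaches 0.10 at p = 16.3%, which is 1.3 points above the stated null. It is 0.092 at 16%, 0.149 at 18% and 0.220 at 20%.

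**4. Scenario A: surveillance adds risk independently to 15%.** For an untreated rate r per 6 months, constant over time, and m months of surveillance, s = 1 − (1 − r)^(m/6) and p = 1 − 0.85(1 − s). For r = 10% and m = 2, s = 1 − 0.9^(1/3) = 0.0345 and p = 1 − 0.85 × 0.9655 = 0.179.

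| r per 6 months | P(X ≥ 7), 2 months | 3 months | 4 months |
|---|---|---|---|
| 10% (plan's figure) | 0.1466 (p = 17.9%) | 0.1958 (19.4%) | 0.2505 (20.8%) |
| 5% (assumed) | 0.1032 | 0.1228 | 0.1442 |
| 2% (assumed) | 0.0819 | 0.0885 | 0.0954 |

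**5. Scenario B: one untreated rate over the whole period.** Applying 10% per 6 months to surveillance plus 7 treatment months, p = 1 − 0.9^(months/6):
- 9 months: 14.6%, P(X ≥ 7) = 0.062
- 10 months: 16.1%, 0.095
- 11 months: 17.6%, 0.135

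**6. No surveillance.** For men who go straight to C1D1 with no earlier values scored, nothing is added. If this holds for all 25, the error at a true null of 15% stays at 0.0695.

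**The case against.** **The 15% may not belong to the treatment window.** This stands in part. No derivation is given, and 10.2 also says that participants may be followed for an extended period with the endpoint reached at any point in it. The link to treatment rests on the definition in the same section. But the plan does not justify 15% for the on-study window either.

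**Scenario A combines two rates that do not agree.** This stands. At 10% per 6 months, 7 untreated months give 1 − 0.9^(7/6) = 11.6%, not 15%. Scenario B uses one rate throughout, and alpha then stays below 0.10 for 2 or 3 months of surveillance.

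**A surveillance fall is often cancelled.** A reader might infer that any man with a 30% fall in surveillance becomes a vaccine responder. The documents do not support this. Section 2.1.3 requires a doubling time of 5 to 15 months. If growth resumes at that pace, a 30% fall is regained in log2(1/0.7) = 0.515 doubling times, which is 2.6 to 7.7 months, and within the 7 treatment months for doubling times below 7/0.515 = 13.6 months. Once a higher, validated value appears, the apex moves into treatment and the earlier fall no longer counts. Scenario A ignores this.

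**Few men may be affected.** Section 2.1.3 also requires rising PSA, which selects against men whose PSA is already falling. Surveillance is given only as needed in Arm 3 (2.3.1), and since the 05/10/2023 amendment it stops once three adequate values exist. This limits the effect but does not remove it: a peak late in surveillance can still be the apex from which a fall is measured.

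**Conclusion.** The contradiction is in the text and needs no model: 10.2 uses treatment values, while 3.1, 6.3.2, 10.4.1 and 10.4.2 admit surveillance values, including some from before enrolment. A fall that starts or is completed before C1D1 can count, provided later PSA does not rise above the surveillance peak. For an ordered maximum and minimum, the bias can only favour the vaccine.

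The size is conditional. The rule has little slack, since about 1.3 points of extra null response use up the nominal 0.10. Independent addition to 15% at the plan's 10% per 6 months gives 0.147 to about 0.25 for 2 to 4 months, or 1.5 to 2.5 times 0.10. At 5% it gives 0.103 to 0.144, and at 2% it gives 0.082 to 0.095, within the nominal level. One rate over 9 to 11 months gives 0.062 to 0.135. These are scenarios, not bounds.

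A reader might infer that an inactive vaccine would pass two to four times as often as designed. The documents do not support that. Such a ratio divides the top row of Scenario A by the attained 0.0695 and not by the designed 0.10. It also depends on adding the two risks as independent and on reading a planning input for another comparison as an observed rate of falls.

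**What to change.** Use one window for the primary response in 3.1, 6.3.2, 10.2, 10.4.1 and 10.4.2:

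- The apex is the highest validated PSA at or after C1D1, with the C1D1 value included.
- The two consecutive confirming values, at least 30% lower, must come after that apex.
- State one end of the window in all these sections, for example the end-of-treatment visit, to match the treatment window in 10.2. A start at C1D1 alone is not enough, because the on-study window also runs into follow-up.
- Use surveillance and pre-enrolment values only to validate the C1D1 value within 10% and for baseline kinetics. Delete the statement in 3.1 that they enter the apex for the primary endpoint.
- Report falls that began or were complete before C1D1 descriptively.

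Keeping the full on-study window with a null justified for it would repair the error rate, but it would still credit falls before the first dose to the vaccine.

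**Cost.** Wording only, with no new visits or data, provided it is settled before the primary analysis. The observed response rate may be slightly lower, because a man who peaked in surveillance loses the part of his fall that came before C1D1. Responses first seen after the window closes would be reported separately.

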3.1.1 Safety Assessment

For safety purposes, a minimum of 6 weeks must elapse between C1D1 of the third participant enrolled and C1D1 of the fourth participant enrolled which will allow for an adequate toxicity evaluation period of the combination therapies (i.e., 3 participants will have received combination vaccine and anti-PDL1 TGF β Trap before any additional participants will be treated with that combination).

3.2 DRUG ADMINISTRATION

3.2.1 Prostvac

- The Prostvac vaccine regimen consists of Prostvac-V (priming vaccine) and Prostvac-F (booster vaccine).
- Prostvac will be administered nearly identical to the Phase III regimen with Prostvac-V (2×10^8 infectious units per 0.5 mL) given day 1 (week 1) followed by Prostvac-F (1×10^9 infectious units per 0.5 mL) on weeks 3 and 5 then monthly for an additional 5 months.
- Prostvac is administered subcutaneously preferably in the upper thigh. Alternate subcutaneous sites may be used with approval of the principal investigator.
- Prostvac should be handled according to the guidelines outlined by each department. Study staff administering the vaccine or assessing the vaccine site should wear personal protection consistent with the standard of practice outlined by each department or unit. Participants receiving Prostvac-V should be isolated just prior to the administration of

vaccine and can be removed from isolation after the vaccine is administered and an appropriate sterile dry dressing is secured over the injection site.

- Participants should be provided with the Vaccinia-Prostvac Participant Instruction Sheet at the time of or prior to administration of Prostvac-V ([APPENDIX B](#)).

3.2.2 CV301

- The CV301 vaccine regimen consists of MVA-BN-CV301 (priming vaccine) and FPV-CV301 (booster vaccine).
- MVA-BN-CV301 is administered as four subcutaneous injections (4×10^8 infectious units/0.5 mL each) on C1D1 and C1D15 followed by FPV-CV301 (1×10^9 infectious units/0.5mL) administered on C2D1 then monthly for an additional 5 months.
 - MVA-BN-CV301 is administered as one injection in each of the following locations: upper left arm, upper right arm, upper left thigh and upper right thigh (i.e., four injection sites per dose). Alternate subcutaneous sites may be used with approval of the principal investigator.
 - FPV-CV301 is administered as a subcutaneous injection preferably in the upper arm (i.e., one injection site per dose). An alternate subcutaneous site may be used with approval of the principal investigator.

3.2.3 MSB0011359C

Effective with amendment v7/29/2021, MSB0011359C will no longer be given as part of the treatment combination for the Biochemical Recurrence cohort (Arms 2 and 3).

- MSB0011359C (anti-PDL1 TGF β Trap) will be administered at a dose of 1200mg by IV infusion over 60 minutes every 2 weeks for 3 months (6 doses) starting after 4 months of concurrent Prostvac and CV301. Use of an in-line 0.2 or 0.22 micron filter during infusion administration is required.
- Current experience revealed that infusion related reactions (IRRs) to MSB0011359C seldom occur and are generally mild to moderate in severity. Therefore, administration of a premedication is generally not required.
 - If an Investigator deems it necessary to administer a premedication to a particular participant, an antihistamine (e.g., diphenhydramine 25-50mg and acetaminophen 650mg intravenously or equivalent oral dose) is recommended approximately 30 - 60 minutes prior to the MSB0011359C infusion. If Grade \geq 2 infusion reactions are seen during the first two infusions, premedication should not be stopped. Premedication regimens may be adjusted based on local site procedures or participant-specific factors. Steroids as premedication are not permitted.
- Infusion-related reactions to MSB0011359C
 - Participants experiencing a grade 4 infusion related reaction will have the infusion stopped immediately and will not be rechallenged.

- Participants experiencing a \geq grade 2 infusion related reaction will have the infusion duration extended to 120 minutes for remainder of that infusion and all subsequent infusions.
- MSB0011359C should be administered in a setting that allows for immediate access to an intensive care unit or equivalent environment and administration of therapy for anaphylaxis, such as the ability to implement immediate resuscitation measures. Steroids (dexamethasone 10 mg), epinephrine (1:1,000 dilution), allergy medications (IV antihistamines), bronchodilators, or equivalents, and oxygen should be available for immediate access.

